#### 9.6 Efficacy Subgroup Analyses

The percentages of live female adult worms without *Wolbachia* out of all live female adult worms from subjects in the PP population will be summarized by treatment arm for each category of the following subgroup variables, after applying the rules of Section 9.2 for missing data. 95% Wilson's score confidence intervals will be provided for all the percentages if the denominator is  $\geq 10$ . The rules of Section 9.2 for imputing missing data in the PP population worms will be applied; any worms that still have missing *Wolbachia* status after that will be excluded from both the numerator and denominator. The subgroup variables include:

- Operable sites with onchocercomata (0, 1, or > 1),
- Baseline skin microfilarial density ( $\leq 5 \text{ or} > 5 \text{ mf/mg}$ ),
- Number of previous ivermectin rounds (0, 1, or > 1)
- Time since the last ivermectin administration ( $\leq 1$  year or > 1 year)
- District of residence (Kimpese, Masa, Masi-Manimba, Moanza, Nsonampangu, Pay Kongila, or Other)

The different treatment effects across these subgroup variables will be further explored using the alternating logistic regression model detailed in Section 9.3.2. The continuous values of the subgroup variables will be used except for district of residence. Each subgroup variable will be added separately to the model as a factor in addition to the treatment arms. Then, the interaction term of the subgroup variable with the treatment arms will be included in addition to the main effect term and analyzed in a separate model to examine the effect of the subgroup variables on treatment efficacy.

# 10.0 Safety Analyses

#### 10.1 General Considerations

Safety data will be summarized for the Safety population in Part 1. If any of Arms A B C, D was closed during the study and any of Arms F, G, H, I was opened, all individual treatment arms will be included in the safety analyses. All safety summaries will be presented by treatment arm, as well as for all subjects taking ABBV-4083 (i.e., combining Arms A, B, C, D, as well as, F, G, H, I, if applicable). For the safety analyses, a subject's treatment arm will be determined based on the treatment arm assigned at randomization.

#### 10.2 Adverse Events

Adverse events (AEs) will be summarized and presented using primary MedDRA System Organ Classes (SOCs) and preferred terms (PTs) according to the version of the MedDRA coding dictionary used for the study at the time of database lock. The actual version of the MedDRA coding dictionary used will be noted in the AE tables and in the clinical study

report. Specific PTs will be counted once for each subject for calculating percentages, unless stated otherwise. In addition, if the same PT occurs multiple times within a subject, the highest severity and level of relationship to investigational product will be reported.

#### 10.2.1 Treatment-Emergent Adverse Events

Treatment-emergent AEs are defined as any AE with the onset date that is after the first dose of study drug and no more than 30 days after the last dose. Events with the same onset date as the study drug start date are assumed to be treatment-emergent. All treatment-emergent AEs will be summarized overall, as well as by primary MedDRA SOC and Preferred Term. The SOCs will be presented in alphabetical order, and the PTs will be presented in alphabetical order within each SOC. The number and percentage of subjects experiencing treatment-emergent AEs will be summarized.

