9.2.4.1 Procedures routinely to be performed before IMP administration

- Collection of pre-dose AEs (see Section 9.3.4).
- Collection of pre-dose concomitant medications (see Section 8.1 and 9.3.1.3)
- Laboratory safety, including haematology, biochemistry and urinalysis (see Section 9.3.3.9.1)
- Pregnancy test in WOCBP (see Section 9.3.3.9.3)
- Collection of exploratory samples
- Pre-dose PK blood sampling (see Section 9.3.2)
- Vital signs (see Section 9.3.3.6)

The IMP must be administered to subjects with food (see Section 9.2.8), except for ivermectin or matching placebo at Month 6 in Part 2, which must be administered in the fasting state.

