9.3.4.2 Assessment of Abnormalities from Laboratory Tests or Other Procedures

For every laboratory test/procedure, the Investigator will evaluate if the result of the laboratory test/procedure is normal or abnormal. If abnormal (after repeat testing, if indicated), the Investigator will assess whether the finding is "clinically significant" or not. An abnormal result on a laboratory test/procedure must be compared with the previous value taking into account normal values in the studied population/country.

If the result of a laboratory test/procedure is abnormal and the abnormality assessed as clinically significant, it should be reported as an AE.

Abnormalities on laboratory tests/procedures (e.g. ECG) or worsening in severity or frequency of pre-existing abnormalities should be assessed as "clinically significant" and therefore must be reported as AE if they meet at least one of the following conditions:

- The abnormality suggests a disease and/or organ toxicity and this abnormality was not present at the screening visit or is assessed as having progressed since the screening visit;
- The abnormality results in discontinuation of the IMP;
- The abnormality requires medical intervention or concomitant therapy.

When reporting an abnormal result on laboratory test/procedure as an AE, a clinical diagnosis should be recorded rather than the abnormal value itself, if available (e.g. acute pancreatitis instead of each finding separately: high levels of amylase, high levels of lipase, abdominal pain

and vomiting; e.g. "hypokalaemia" rather than "decreased potassium levels"; "anaemia" rather than "decreased red blood cell count).

An event that occurs after signature of the ICF and prior to the first IMP administration is not considered an AE per se but as an "event" that could be due to the disease or specific circumstances in which the subject has been placed (e.g. "protocol related" which may be caused by the participation to the trial).

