9.3.4.4 Eliciting Adverse Event Information

The Investigator is required to report all directly observed AEs and all AEs spontaneously reported by subjects using concise medical terminology.

In addition, to avoid bias in eliciting AEs, subjects will be questioned about the occurrence of AEs at the time-points indicated in the Schedules of Events (see Appendix 1. and Appendix 2. Schedule of Events in Part 2), with general non-leading questions such as "Since xxx (e.g. last visit) have you had any health problem?" or "How are you feeling?".

All AEs (serious and non-serious) must be recorded on the source documents and AE pages of the eCRF regardless of the assumption of a causal relationship with the IMP. The definition, reporting, and recording requirements for AEs are described in Section 9.3.4.

Information on AEs must be evaluated by a physician.

Each AE is to be classified by the Investigator as serious or non-serious (see definition of a SAE in Section 9.3.4.3). This classification will determine the reporting procedure for the event.

In addition, the frequency, seriousness, severity (see Section 9.3.4.6) and causality (see Section 9.3.4.7) assessment of AEs will be described.

Non-serious AEs are to be recorded in the eCRF, including description of the event, onset date, end date, severity, seriousness, relationship to all study drugs, actions taken and outcome. Start and stop times are to be recorded when available during the in-house period in order to capture Treatment Emergent Adverse Event (TEAE).

Only one AE and the maximum severity will be recorded in the eCRF for each separate event. If the AE resolves but then recurs, each will be recorded as a separate AE, with the appropriate start and stop times.

SAEs will be reported both on the AE page of the eCRF and the SAE forms.

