9.3.4.5 Adverse Event Reporting Period

In this protocol, the reporting period is different for AEs and for SAEs:

- Non-serious AEs: all non-serious AEs will be reported from administration of the first intake of IMP until the subject's end of study participation (see Section 3.4). Furthermore, non-serious events that occur in the screening period (from signature of the ICF) until before the first intake of the IMP and that are judged as related to study participation (e.g. haematoma due to venipuncture, wound infection due to skin snips), will be recorded on the AE page of the eCRF.
- SAEs: all SAEs must be reported after signature of the ICF during the screening period until the subject's end of study participation (as defined in Section 3.4) on the AE page of the eCRF and the SAE form.

All treatment emergent AEs that occur during the AE reporting period as defined in this section must be reported, whether or not the event is considered treatment related.

In addition, any SAE that occurs after the end of the AE reporting period and that the Investigator assesses as possibly, probably or definitely related to the IMP or to participation in the study may also be reported as an SAE.

Screening failure: beyond the date of screening failure (to be recorded), only serious study-related events will be reported.

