10.8 Statistical Analysis of Safety

All safety analyses will be performed on the Safety Population, which consists of all subjects who received at least one dose of IMP. Safety will be assessed by AEs, laboratory tests, vital signs, and ECG variables. Details of the analyses will be provided in the Statistical Analysis Plan.

AEs will be coded using the Medical Dictionary for Regulatory Activities (MedDRA). A TEAE is defined as an AE with an onset date that is after the first intake of IMP and no more than 30 days after the last intake of IMP. The number and percentage of subjects experiencing TEAEs will be tabulated using MedDRA system-organ class and preferred term, as well as by severity and by relationship to the IMP as assessed by the Investigator. Summaries of SAEs, deaths, AEs leading to discontinuation will also be provided.

For laboratory test and vital signs variables, mean change from baseline and percentage of subjects with on-treatment laboratory values of CTCAE 5.0 adapted scale grade 3 or 4 will be summarised.

10.9 Interim Analysis of Part 1 and DSMB Recommendation to Proceed to Part 2

Once subjects in Part 1 have completed or prematurely discontinued the study, up to and including nodulectomy at 6 months, a database lock for Part 1 database and an interim analysis of data from Part 1 will be conducted by the Sponsor and the randomisation code unblinded. The unblinded data will be reviewed by the Sponsor and the DSMB (see Section 13.3), for futility and risk/benefit ratio. Taking into account the recommendations of the DSMB, especially regarding the safety assessment of the data, the Sponsor will decide whether or not to proceed to Part 2, and with which dose regimens.

Selection of up to two acceptable/suitable doses / regimens for Part 2 will be based on analysis of all of available unblinded data from Part 1, including safety and tolerability of ABBV-4083 and ABBV-4083 + albendazole, *Wolbachia* depletion, disruption of embryogenesis and an exploratory surrogate marker, microfilaria *Wolbachia*, observed at Months 3 and 6.

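### SAP 10.2.1 counts a Day 0 event as treatment-emergent even when its recorded start time is before the first dose; the over-count is small and non-differential, and one sentence would fix it

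*SAP*

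**What the plan says.** SAP Section 10.2.1 begins with a definition: "Treatment-emergent AEs are defined as any AE with the onset date that is after the first dose of study drug", up to 30 days after the last dose. It then adds the rule for the first day: "Events with the same onset date as the study drug start date are assumed to be treatment-emergent". The rule is not restricted to events with a missing or partial start time.

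Protocol Section 10.8 has a matching definition, "A TEAE is defined as an AE with an onset date that is after the first intake of IMP", and no rule for events on the same day.

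Three other parts of the protocol bear on Day 0:

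- **Status of pre-dose events (Section 9.3.4.2):** "An event that occurs after signature of the ICF and prior to the first IMP administration is not considered an AE per se".
- **Start times (Section 9.3.4.4):** "Start and stop times are to be recorded when available during the in-house period in order to capture Treatment Emergent Adverse Event (TEAE". The rationale table for Protocol Amendment 1 gives the same purpose for adding these times.
- **What reaches the AE page (Section 9.3.4.5):** it covers "non-serious events that occur in the screening period (from signature of the ICF) until before the first intake of the IMP", provided they are judged related to study participation, with a venipuncture haematoma as an example. For serious events, "all SAEs must be reported after signature of the ICF during the screening period".

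**The concern.** Day 0 is the one day on which the date cannot say whether an event came before or after the first dose and a clock time can. The protocol arranges for that time to be recorded. The SAP then assigns the whole day to the treatment-emergent period, including events that the record itself places before treatment.

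An event that precedes any exposure cannot be an effect of treatment. Counting it raises the TEAE percentage in every arm by a common background. With 30 subjects per arm, and with regimen choice for Part 2 drawing on safety and tolerability (Protocol Section 10.9), the TEAE tables should not contain events that the trial's own data can identify as pre-dose.

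The departure is also undeclared. SAP Section 1.0 states that the analyses agree with the protocol unless Section 13.0 notes otherwise, and the version history there does not mention the same-day rule.

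**Working it through.** The plan gives no figure to reproduce. The check compares the texts and then illustrates the size over a range.

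**Step 1. Do the rules differ?** Take an event on Day 0 with a recorded start time before the first dose.

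- Protocol Section 10.8: onset is not after the first intake, so it is not a TEAE.
- Protocol Section 9.3.4.2: it is an event, not an AE as such.
- SAP Section 10.2.1: its date equals the study drug start date, so it is a TEAE.

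The classifications conflict for this case. They need not conflict when the time is missing, because the protocol's definition then cannot be applied within the day and some default is needed.

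**Step 2. Can such an event reach the tables?** Yes, by a narrow route.

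- Protocol Section 9.3.4.5 admits two kinds of pre-dose event to the AE page: participation-related non-serious events, and serious events.
- Blood is drawn before the Day 0 dose. Footnote 21 to Table 7 (Appendix 1) sets a 0 h pharmacokinetic sample at any time before dosing. Optional exploratory samples are also due on Day 0, and Section 9.2.4.1 lists them among the pre-dose procedures.
- The AE fields listed in Section 9.3.4.4 include no pre-dose flag. The start time is what would separate these records.

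A haematoma from the 0 h draw, timed before the dose, would enter the any-TEAE row of SAP Section 10.2.2. A serious pre-dose event on Day 0 in a subject who was then dosed would enter the serious TEAE row.

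**Step 3. How large could it be?** The documents do not say how many such events to expect, so every rate here is an assumption. Let p be the true TEAE rate and f the proportion of subjects with a recorded pre-dose event on Day 0, independent of p.

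- Tabulated rate = 1 − (1 − p)(1 − f)
- Extra subjects per arm of 30 = 30 × f × (1 − p)

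With illustrative true rates of 20% in an active arm and 10% in the control arm:

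| f | Active rate | Control rate | Extra subjects, active | Extra subjects, control | Difference | Ratio |
|---|---|---|---|---|---|---|
| 0 | 20.0% | 10.0% | 0 | 0 | 10.0 points | 2.00 |
| 1% | 20.8% | 10.9% | 0.24 | 0.27 | 9.9 points | 1.91 |
| 2% | 21.6% | 11.8% | 0.48 | 0.54 | 9.8 points | 1.83 |
| 5% | 24.0% | 14.5% | 1.20 | 1.35 | 9.5 points | 1.66 |

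For f = 5%: 1 − 0.80 × 0.95 = 0.240; 1 − 0.90 × 0.95 = 0.145; 0.240 / 0.145 = 1.66; 30 × 0.05 × 0.90 = 1.35.

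In the arm with the lower true rate, the addition runs from about 0.3 subjects (f = 1%) to about 1.4 (f = 5%). The 5% end is probably high, because only the two kinds of event in Step 2 qualify.

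**The case against.** The case for leaving the rule alone is reasonable, and most of it stands.

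- **A tie rule is needed.** The protocol's own definition speaks of an onset date, which cannot order events within Day 0. The toxicity criteria in Protocol Section 3.5.2.2 also run from Day 0 as a whole day. The SAP's choice over-counts rather than hides events. This justifies a default, but not overriding a time that has been recorded.
- **Times are incomplete.** They are recorded only when available. Amendment 1 was written after 57 subjects had been randomised, so earlier times may be absent. The default must therefore stay for those events.
- **Day 0 offers few occasions.** Table 7 schedules no skin snips or laboratory safety tests that day, and six of the seven Day 0 pharmacokinetic samples are post-dose. Many Day 0 haematomas would follow the dose or have no clear order. This limits the size but does not remove the case.

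Three stronger readings are tempting and are not supported:

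- **That the rule distorts a planned between-arm comparison.** The ratio in the working does move toward 1, but the synopsis describes the safety analysis as descriptive, and SAP Section 10.2 plans counts and percentages, with no risk ratio or test of TEAE rates. The difference moves by at most half a point in the illustration.
- **That all pre-dose events become TEAEs.** Protocol Section 9.3.4.5 restricts which ones are recorded on the AE page.
- **That "Collection of pre-dose AEs" in Protocol Section 9.2.4.1 shows a dedicated separation before the first dose.** That list covers every dosing day. After Day 0, an event before that day's dose still follows the first dose and is properly a TEAE.

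**Conclusion.** The point holds in a limited form. As written, SAP Section 10.2.1 classes an event known to precede the first dose as treatment-emergent. That contradicts the protocol's definition and leaves the recorded start times unused on Day 0.

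The effect is a small over-count that, under double-blind randomisation, should not systematically favour any arm. The figure of about 0.3 to 1.4 subjects per arm rests on an assumed 1% to 5% of subjects affected, on the illustrative 10% true TEAE rate, and on independence between pre-dose and later events.

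No efficacy result is affected. A procedure-related event judged unrelated to study drug does not enter the drug-related tables, and the AE toxicity criteria require a relation to the IMP, so both are little affected. A reader might infer biased safety conclusions or wrongly triggered dose changes; the documents support neither. This is a worthwhile tidying of the SAP, not a threat to the trial's conclusions.

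**What to change.** Replace the same-day sentence in SAP Section 10.2.1 with wording to this effect: *An event dated on the day of first dosing is classified by its recorded start time relative to the time of the first dose. It is assumed to be treatment-emergent if either time is missing or the order cannot be established. Events known to have started before the first dose are listed separately.*

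If the sponsor prefers the date-only rule, it should be declared in SAP Section 13.0 as a departure from the protocol.

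The cost is one SAP sentence, one listing and a small programming change. The practical condition is that first-dose time must be available to the analysis. Protocol Section 9.3.2 places dosing times in the medical file and/or eCRF, so the sponsor should confirm that the time is in the database. Where it is not, the present default continues to apply.

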#### 10.2.2 Adverse Event Overview

An overview of AEs will be presented consisting of the number and percentage of subjects experiencing at least one event for each of the following AE categories:

- Any treatment-emergent AE;
- Any treatment-emergent AE related to study drug (ABBV-4083, albendazole, ABBV-4083 and/or albendazole, and ABBV-4083 and albendazole) according to the investigator;
- Any Grade 3 or higher treatment-emergent AE (or if an AE is not graded as such, using maximum severity instead and including AEs that are severe, life-threatening, or led to death);
- Any serious treatment-emergent AE;
- Any serious treatment-emergent AE related to study drug (ABBV-4083, albendazole, ABBV-4083 and/or albendazole, and ABBV-4083 and albendazole) according to the investigator;
- Any treatment-emergent AE leading to discontinuation of study drug (ABBV-4083, albendazole, ABBV-4083 and/or albendazole, and ABBV-4083 and albendazole);

- Any treatment-emergent AE leading to death;
- All deaths during the study, deaths occurring prior to or at 30 days after the last dose, and deaths occurring > 30 days after the last dose.

#### 10.2.3 Treatment-Emergent Adverse Events by SOC and/or PT

Treatment-emergent AEs will be summarized by SOC and PT; by maximum relationship to study drug as assessed by the investigator and SOC and PT; by maximum grade/severity and SOC and PT; and by subject number and SOC and PT. Specific PTs will be counted once for each subject for calculating percentages, unless stated otherwise. In addition, if the same PT occurs multiple times within a subject, the highest grade/severity and level of relationship to investigational product will be reported. The relationship to study drug will be collected as "definitely related," "probably related," "possibly related," "probably not related" and "not related," but it will be summarized as "related" (combining "definitely related," "probably related," and "not related" (combining "probably not related" and "not related"). Summaries of treatmentemergent AEs by maximum relationship to study drug, SOC and PT will be performed separately by relationship to ABBV-4083, relationship to albendazole, relationship to ABBV-4083 and albendazole, and relationship to ABBV-4083 and/or albendazole.

For the summary of treatment-emergent AEs, the maximum severity is determined by using reported per CRF severity as mild, moderate, severe, life-threatening, and death; CTCAE grades 1-5 as categories mild, moderate, severe, life-threatening, and death; or Vaccine Trial grades 1-4 as categories mild, moderate, severe, and life-threatening.

In addition, treatment-emergent adverse events will be summarized by PT and sorted by decreasing frequency among all subjects taking ABBV-4083.

#### 10.2.4 SAEs (Including Deaths) and Adverse Events Leading to Study Drug Discontinuation

Treatment-emergent SAEs (including deaths) and AEs leading to study drug discontinuation (ABBV-4083, albendazole, ABBV-4083 and albendazole, and

ABBV-4083 and/or albendazole) will be summarized by SOC and PT and in listing format. Listings of all SAEs and all deaths during the study will also be provided.

#### 10.3 Analysis of Laboratory Data

Haematology variables to be summarized include: haematocrit, haemoglobin, red blood cells (RBC), white blood cells (WBC), neutrophils, lymphocytes, monocytes, eosinophils, basophils, platelets.

Chemistry variables to be summarized include: aspartate aminotransferase (AST), alanine aminotransferase (ALT), alkaline phosphatase (AP), glucose, creatinine, eGFR, blood urea nitrogen (BUN), total bilirubin, albumin, total protein, chloride, sodium, potassium and calcium.

Each laboratory variable will be summarized for all time points (Baseline, Day 3, Day 6, Day 13, Month 3, and end of study follow-up) with the number of non-missing observations, mean and standard deviation, median, Q1, Q3, minimum and maximum. Mean change from baseline to each applicable post-baseline visit will be summarized for all laboratory variables, with the number of observations, baseline mean, and visit mean. The change from baseline mean, standard error, and 95% confidence interval will be presented for the mean change from baseline within each treatment arm and difference between the active arms and the control arm (A, B, C, D vs. E) and between all active arms and the control arm (A – D vs. E) using separate ANOVA models.

Changes in chemistry and hematology laboratory parameters will be tabulated using shift tables, for laboratory parameters that have a normal range reported. Laboratory data values will be categorized as low, normal, or high based on the normal ranges of the laboratory used for each sample. Shift tables from baseline to the minimum and maximum values during the Treatment Period will be created. In these shift tables, the number and percentage of subjects with baseline values within or above the normal range (baseline high or normal) and a minimum value below the normal range (post-baseline low during treatment) and the number and percentage of subjects with baseline values within or

below the normal range (baseline low or normal) and a maximum value above the normal range (post-baseline high during treatment) will be summarized. Similar shift tables will be created for the shift from baseline to the final post-baseline value where the number and percentage of subjects with baseline values within or above the normal range (baseline high or normal) and the final post-baseline value below the normal range and the number and percentage of subjects with baseline values within or below the normal range (baseline low or normal) and the final post-baseline value above the normal range (baseline low or normal) and the final post-baseline value above the normal range will be summarized.

The number and percentage of subjects with a maximum of Grade 3, a maximum of Grade 4, and a maximum of at least Grade 3 (CTCAE 5.0) for the laboratory parameters during treatment as defined in Appendix C will be summarized. The post-baseline value must be in a toxicity grade that is more extreme than the toxicity grade corresponding to the baseline value, if a baseline value is available, in order to be counted. A listing of all relevant laboratory parameters will be provided for each subject who had an increase to Grade 3 or higher.

The following criteria will be used to assess potential hepatotoxicity during treatment.

- $ALT > 3 \times ULN, > 5 \times ULN, > 10 \times ULN, > 20 \times ULN$
- $AST > 3 \times ULN, > 5 \times ULN, > 10 \times ULN, > 20 \times ULN$
- bilirubin >  $1.5 \times ULN$ , >  $2 \times ULN$
- ALT and/or AST >  $3 \times$  ULN and bilirubin >  $1.5 \times$  ULN
- ALT and/or AST >  $3 \times$  ULN and bilirubin >  $2 \times$  ULN
- ALT > 3 × ULN and bilirubin >  $1.5 \times ULN$
- ALT > 3 × ULN and bilirubin > 2 × ULN
- Alkaline phosphatase (ALP)  $> 1.5 \times ULN$

The number and percentage of subjects with laboratory values meeting the above criteria during treatment will be summarized. Listing of ALT, AST, total bilirubin, and alkaline phosphatase values will be provided for each subject who met one or more of the criteria defined above.

An Evaluation of Drug Induced Serious Hepatotoxicity (eDISH) plot of the maximum post-baseline ALT value (as a multiple of the ULN) versus the maximum post-baseline bilirubin value (as a multiple of the ULN) during treatment, not necessarily concurrent, will also be utilized to assess for potential hepatotoxicity. A similar plot will be produced for AST versus bilirubin.

